## 1. Background

Sepsis is a high incidence, high morbidity and mortality, life-threatening organ dysfunction caused by a dysregulated response to infection that constitutes a public health priority. Improving sepsis diagnosis and finding pathogenically-relevant targets for pathophysiological therapy are opportunities to reduce sepsis burden.

Despite not being critical to contain microorganisms, granzyme A (GZM A), a serine protease enzyme that is present in cytotoxic T lymphocyte granules might be a pathogenically relevant sepsis mediator. We found that GzmA knocked-out mice had significantly prolonged survival as compared with wild-type mice in an induced polymicrobial peritonitis (cecal ligation and puncture) murine model (Arias et al., 2018. Unpublished data). To the best of our knowledge, the pathogenic role of GZM A in humans with sepsis has been barely explored.

In order to ascertain the pathogenic role of GZM A in sepsis we designed a nested case-control study in patients with bacteremic urinary tract infections caused by *E. coli*. This human model of infection-sepsis homogenizes other factors (patient, infection and microorganism related factors) that could be pathogenically associated with sepsis in order to minimize confounding.

## 2. Research hypothesis

The research team has explored the role of GZM A

- **Conceptual hypothesis:**
  - Granzyme A is a pathogenic sepsis mediator.
  - Granzyme A gene polymorphisms determine the serum concentration of GZM A in patients with systemic infections.
  - Granzyme A gene polymorphisms determine the risk of sepsis among patients with systemic infections.
- **Operational hypothesis:**
  - Among patients with bacteremic (*E. coli*) urinary tract infections (UTIs), GZM A levels are significantly higher in those patients who develop sepsis as compared with those who do not develop sepsis.
  - There are significant differences in the GZM A gene polymorphism profile of patients with bacteremic (*E. coli*) UTIs who develop sepsis as compared with those who do not develop sepsis.

## 3. Aims and objectives

### 3.1. Aims

1. To assess the pathogenic role of GZM A in sepsis in patients with bacteremic (*E. coli*) UTIs.
2. To explore the capability of GZM A polymorphisms to anticipate the risk of

- developing sepsis in patients with bacteremic (*E. coli*) UTIs.
3. To evaluate the potential usefulness of GZM A as a diagnostic biomarker of sepsis in patients with bacteremic (*E. coli*) UTIs.
  4. To characterize *E. coli* "virulome" among circulating uropathogenic strains.

### **3.2. Objectives**

1. To evaluate the correlation between serum levels of GZM A and systemic inflammatory response in patients with bacteremic (*E. coli*) UTIs.
2. To characterize GZM A gene polymorphisms among patients with bacteremic (*E. coli*) UTIs
3. To assess GZM A serum kinetics among patients with bacteremic (*E. coli*) UTIs
4. To phenotypically and molecularly characterize *E. coli* strains causing bacteremic UTIs, including their virulence factors ("virulome").

**Expected outcomes.** Relevance and transformative approach of the proposal.

#### **1. Characterization of the pathogenic role of GZM A in sepsis in patients with systemic infections**

- 1.1. Evaluation of the potential association between GZM A serum levels and sepsis.
  - The association between GZM A serum levels and the extent of systemic inflammatory response is a non-sufficient, albeit necessary condition to establish a pathogenic (causal) relationship between GZM A and sepsis.
- 1.2. Identification of *gzmA* gene polymorphisms associated with an increased risk of developing sepsis among patients with infections:
  - Significant differences in serum GZM A concentrations between patients with and without sepsis would suggest a potential pathogenic role of GZM A.
  - If certain *gzmA* gene polymorphisms are associated with lower sepsis risk through lower GZM A serum levels, *gzmA* based sepsis risk could be estimated so that certain decisions could be personalized.
  - GZM A could be a new potential target for pathophysiological therapy of sepsis.

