## 4. Methods

### 4.1. Design and project scope

- Prospective, exploratory nested case-control study to be conducted at one academic hospital (Hospital Clínico Universitario Lozano Blesa) affiliated with the Instituto de Investigación Sanitaria Aragón (IIS Aragón).

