#### **Exclusion criteria:**

- Use of systemic antibiotics for >48h in the two months preceding the episode.

- Immunocompromised hosts
  - Patients receiving systemic steroid use (>10 mg prednisone/day during 10 or more days in the previous 2 months).
  - Patients receiving biological therapy (previous 2 months).
  - Active solid or hematological cancer.
  - HIV +.
  - Neutropenia < 500 PMN/microl.
- Basal urinary tract abnormalities or locally modified vesical microbiome (any):
  - Ureteroileostomy, ureterosigmoidostomy, ureterostomy (Bricker) or nephrostomy.
  - Indwelling urinary catheter (in the last two months)
  - Urological surgery (in the last two months).
  - Intravesical chemotherapy (in the last two months).
  - Intravesical BCG instillation (in the last two months).

Potential candidates will be detected daily by the microbiologists on the research team. Inclusion criteria will be verified in the multidisciplinary meeting that antimicrobial stewardship teams (AST) conduct on a daily basis at the participating hospital.

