**Estimated size of the study population. Matching:**

- 50 patients with a sepsis/ non sepsis 1:1 ratio will be included.
- Septic and non-septic patients will be matched on gender, age (+/- 10 years), comorbidity (Charlson score +/-1), time symptom onset to blood culture (+/- 24h)

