#### 4.6. Study plan detailing the procedures.

	Day 0	Day 2 - 3	Day 30
Screening (inclusion and exclusion criteria)	X		
Informed Consent	X		
Anamnesis	X		
Charlson Modified	X		
Sepsis score	X	X	
Serum	X	X	X
Plasma	X	X	X
Microbiological samples	X		
Mortality			X
New hospitalization			X

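### Does a 1:1, matched sample of 50 patients undermine the protocol's remark that a gzmA-based sepsis risk could be estimated?

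*Protocol*

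**What the plan says.** Section 4.1 describes a "Prospective, exploratory nested case-control study to be conducted at one academic hospital". Section 4.3 fixes the sampling: "50 patients with a sepsis/ non sepsis 1:1 ratio will be included". It adds: "Septic and non-septic patients will be matched on gender, age (+/- 10 years"), and also on Charlson score and on time from symptom onset to blood culture. Section 4.4 defines cases by the presence of sepsis or septic shock and controls by their absence, so selection is on the outcome.

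The remark at issue stands under Expected outcomes in Section 3.2, item 1.2. It opens with a condition, namely that certain polymorphisms go with lower sepsis risk through lower serum levels. It then says that a gzmA-"based sepsis risk could be estimated so that certain decisions could be personalized". Aim 2 in Section 3.1 is related: "To explore the capability of GZM A polymorphisms to anticipate the risk of" sepsis.

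On the source population, Section 4.3 states: "Potential candidates will be detected daily by the microbiologists on the research team". It continues: "Inclusion criteria will be verified in the multidisciplinary meeting" that the stewardship team holds each day. The schedule in Section 4.6 has a Day 0 row, "Screening (inclusion and exclusion criteria"), placed above informed consent. Section 5 describes routine surveillance of bacteraemia patients that includes a data registry. No section says that eligible episodes will be tallied by sepsis status.

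**The concern.** A case-control sample fixes the proportion of cases. From it one can estimate how common a variant is in septic and in non-septic patients, and hence an odds ratio. The probability of sepsis given the variant also needs the share of eligible episodes that are septic, and a 1:1 sample carries no information on that share. Matching adds a second difficulty, because the controls are not a random draw from all non-septic episodes.

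Personalizing a decision most naturally calls for an absolute risk. The word nested implies a source cohort, but the protocol makes no explicit provision for counting it. If no count were kept during recruitment, no later analysis plan could restore it, and a risk read straight from the 50 patients would reflect the chosen ratio. That is why the point looks like a matter of data collection that cannot be left to the analysis stage.

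**Working it through.** **Inputs.** From Section 4.3: 50 patients at 1:1, so 50 × 1/2 = 25 septic and 25 non-septic, a sample sepsis share of 0.50. The protocol gives no carrier frequency, odds ratio or sepsis share, so the following are assumptions. Since the remark concerns variants with lower risk, take a protective variant: carrier frequency c1 = 0.20 in cases and c0 = 0.40 in controls. Let the source sepsis share π run from 0.10 to 0.60. Pairing is ignored, and carriage is taken as unrelated to the matching factors among non-septic patients.

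**Odds ratio.** (0.20/0.80)/(0.40/0.60) = 0.375. It does not depend on π.

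**Carrier risk.** P(sepsis | carrier) = c1·π / [c1·π + c0·(1 − π)]. Read directly from the sample (π = 0.50) this is 0.10/(0.10 + 0.20) = 33.3%.

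**Interval with π known.** The risk odds are π/(1 − π) × c1/c0, with c1/c0 = 0.5. The standard error of the log ratio is √[0.80/(25 × 0.20) + 0.60/(25 × 0.40)] = √(0.16 + 0.06) = 0.469, so the 95% limits multiply the odds by exp(±1.96 × 0.469), that is by 0.40 and 2.51.

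| Source share π | Carrier risk | 95% interval | Non-carrier risk |
|---|---|---|---|
| 10% | 5.3% | 2–12% | 12.9% |
| 20% | 11.1% | 5–24% | 25.0% |
| 30% | 17.6% | 8–35% | 36.4% |
| 40% | 25.0% | 12–46% | 47.1% |
| 60% | 42.9% | 23–65% | 66.7% |

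The sample figure of 33.3% lies above the weighted interval when π/(1 − π) < exp(−1.96 × 0.469) = 0.40, that is when π is below about 29%. With an odds ratio of 1/3 and 30% carriers in controls, that threshold is about 23%. With a harmful variant (odds ratio 3, 30% carriers in controls) it is about 33%. The direction of the point holds in all three cases; its size depends on what is assumed.

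**Would the remark's condition be met?** For 20% against 40%, the cell counts are 5 and 20 in cases, 10 and 15 in controls. The standard error of the log odds ratio is √(1/5 + 1/20 + 1/10 + 1/15) = 0.645. The 95% interval is exp(−0.981 ± 1.265), or 0.11 to 1.33. In the harmful example it is 0.94 to 9.6. Neither excludes 1, so at these effect sizes an association would not be declared at the 5% level.

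**What a tally would buy.** If π = 20% were itself estimated from an assumed 100 logged episodes, the standard error becomes √[0.22 + 1/(100 × 0.2 × 0.8)] = √(0.22 + 0.0625) = 0.53. The interval for carrier risk widens from 5–24% to 4–26%. Non-carrier risk at that share is 25%, so the interval does not separate the two. Weighting to one overall share also leaves the matching only partly corrected; a full correction needs the matching factors for all eligible episodes.

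**What the plan sets out to estimate.** The operational hypotheses in Section 2 are differences in GZM A level and in polymorphism profile between septic and non-septic patients. Objective 2 in Section 3.2 is to characterize the polymorphisms. Aim 2 is exploratory. None of these is an absolute risk.

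**The case for a change.** The strongest case for a change is that logging eligible episodes is cheap, has to happen while recruitment runs, and cannot be repaired afterwards by an analysis plan. The text also does not confine risk to relative measures, and a genotype-specific figure read straight from the sample would be misleading at low sepsis shares.

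The identification argument stands in full. The claim of irrecoverable loss is weaker. Candidates are detected and verified daily, screening precedes consent and so also covers patients who are not enrolled, and a routine registry of bacteraemia patients exists. Choosing matched controls also requires the team to know sepsis status and the matching factors for the candidates it considers. The protocol does not say whether these records are retained for patients who are not enrolled, so recovery is probable rather than assured. Item 1.2 also opens by speaking of polymorphisms associated with an increased risk, which is relative language that an odds ratio answers.

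**Conclusion.** No change is needed. A sample chosen 1:1 on sepsis and matched cannot by itself give an absolute sepsis risk by genotype: in the illustration, the same 50 patients are compatible with a carrier risk anywhere from 5% to 43%. But the protocol does not plan such an estimate. The sentence is a conditional, forward-looking statement of relevance in an exploratory study, and the contrasts that are planned are unaffected by the sampling ratio. Followed as written, the plan gives sound results.

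Keeping a tally of eligible episodes by sepsis status, with the matching factors, would be good practice. So would reading the sentence as referring to odds ratios only. Either is optional: the records probably exist already, and 50 patients would not support individual prediction even with the share known.

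All magnitudes rest on assumed carrier frequencies and sepsis shares and are illustrative. The conclusion would change if an analysis plan or report set out to present genotype-specific sepsis probabilities from these 50 patients without an external sepsis share.

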#### **2. Characterization of GZM A as a sepsis biomarker in a human model of infection-sepsis.**

- 2.1. Evaluation of GZM A kinetics in the aforementioned human model of infection-sepsis:
  - If the GZM A serum level is found to be sensitive and specific enough, determination of GZM A could assist diagnostic and therapeutic decisions in patients with suspected sepsis, which indeed is a difficult-to-diagnose entity due to its common non-specific presentation.
  - The correlation between serum concentration of GZM A and the clinical course

of the infection could assist therapeutic decisions, such as antibiotic streamlining, the switch from sequential intravenous to oral antibiotics and establishing the optimal duration of antibiotic therapy.

### 3. Phenotypical and molecular characterization of uropathogenic *E. coli* causing bloodstream infections:

- Phenotypic and molecular characterization of *E. coli* isolates involved in bacteremic UTIs has a great epidemiological interest
  - Identification of patients infected with hypervirulent strains could potentially influence the monitoring and therapeutic approach.
- Discrimination of *E. coli* isolates according to their virulence (virulome)/potential pathogenicity is important to exclude strain-specific factors, when trying to establish the causal/pathogenic relationship between GZM A and sepsis.

## 4. Methods

### 4.1. Design and project scope

- Prospective, exploratory nested case-control study to be conducted at one academic hospital (Hospital Clínico Universitario Lozano Blesa) affiliated with the Instituto de Investigación Sanitaria Aragón (IIS Aragón).

### 4.2. Study period: June 2019 – December 2020.

### 4.3. Patients and sample size

#### **Inclusion criteria (To meet all):**

- Age  $\geq$  18 years old.
- *E. coli* bloodstream infection
- Urinary source. Urinary source should be considered if (any)
  - Urinary source is clinically suspected and both *E. coli* isolates (in blood and in urine culture) share the same phenotype (antibiogram).
  - Urinary source/origin is clinically suspected, and the urine culture is negative, but the patient had received at least one dose of any systemic antibiotic with antimicrobial activity against the *E. coli* strain causing the BSI before blood cultures were obtained.
  - Both isolates (in blood and in urine culture) share the same phenotype (antibiogram) and there is no alternative source.

#### **Exclusion criteria:**

- Use of systemic antibiotics for >48h in the two months preceding the episode.

- Immunocompromised hosts
  - Patients receiving systemic steroid use (>10 mg prednisone/day during 10 or more days in the previous 2 months).
  - Patients receiving biological therapy (previous 2 months).
  - Active solid or hematological cancer.
  - HIV +.
  - Neutropenia < 500 PMN/microl.
- Basal urinary tract abnormalities or locally modified vesical microbiome (any):
  - Ureteroileostomy, ureterosigmoidostomy, ureterostomy (Bricker) or nephrostomy.
  - Indwelling urinary catheter (in the last two months)
  - Urological surgery (in the last two months).
  - Intravesical chemotherapy (in the last two months).
  - Intravesical BCG instillation (in the last two months).

Potential candidates will be detected daily by the microbiologists on the research team. Inclusion criteria will be verified in the multidisciplinary meeting that antimicrobial stewardship teams (AST) conduct on a daily basis at the participating hospital.

**Estimated size of the study population. Matching:**

- 50 patients with a sepsis/ non sepsis 1:1 ratio will be included.
- Septic and non-septic patients will be matched on gender, age (+/- 10 years), comorbidity (Charlson score +/-1), time symptom onset to blood culture (+/- 24h)

**4.4. Definitions**

Cases (sepsis / septic shock):

- Sepsis or shock septic are defined as life-threatening organ dysfunction caused by a dysregulated host response to infection according to the 2011 SCCM/ESICM/ACCP/ATS/SIS International Sepsis Definition Conference.

Controls:

- Absence of sepsis or septic shock according to the 2011 SCCM/ESICM/ACCP/ATS/SIS International Sepsis Definition Conference.

**4.5. Variables**

- Patient-related variables:
  - Demographical: gender, age.
  - Comorbidity: Modified Charlson Index
  - Baseline serum creatinine.
- Infection-related variables.
  - Time from the onset of symptoms to the start of antimicrobial treatment.
  - Time from the onset of symptoms to the start of appropriate antimicrobial

treatment.

- Time from the onset of symptoms to the surgical therapy (if needed).
- Clinical severity at time 0 (blood culture), and day 2- 3 and day 30: sepsis score.

- Inflammation, sepsis mediators and biomarkers.

The following biomarkers will be determined during patient enrollment:

- White blood cell count and differential.
- Platelet count.
- Fibrinogen.
- Prothrombin activity.
- C reactive protein.
- Procalcitonin.
- GZM A.

GZM A serum levels will be obtained in all patients during the enrollment visit, the 2-3 day and the 30 day visits (GZM A kinetics). GZM A levels will be determined by an ELISA commercial assay (Human Granzyme A ELISA development kit{HRP}; Mabtech).

GzmA gene polymorphisms, as well as other potentially associated mutations, will be screened by Whole Exome Sequencing (WES). To this aim, we will use DNA isolated from peripheral blood cells and the AmpliSeq technology kit on the Ion Torrent platform following the manufacturer's instructions. This platform is available at the Genomics Central Research Unit (CRU) at CIBA from University of Zaragoza/IIS Aragon. All kits for isolating and analyzing DNA samples are commercially available and optimized by Thermo Scientific. Bioinformatic analysis will be performed by an agreement established between Genomics CRU and Micromics SL led by [name] at CRG in Barcelona.

- Microbiological variables
  - Minimum inhibitory concentrations (MIC) of the *E. coli* isolates retrieved from urine and blood cultures will be determined through automated microdilution panels as routinely performed by the Microbiology Laboratory of participating hospitals.
  - Whole genome sequencing (WGS) of the *E. coli* strains isolated in blood and urine cultures. The presence of *E. coli* known virulence factors will be analyzed and a virulence score for each strain will be calculated (Mora-Rillo et al., 2015).

#### 4.6. Study plan detailing the procedures.

	Day 0	Day 2 - 3	Day 30
Screening (inclusion and exclusion criteria)	X		
Informed Consent	X		
Anamnesis	X		
Charlson Modified	X		
Sepsis score	X	X	
Serum	X	X	X
Plasma	X	X	X
Microbiological samples	X		
Mortality			X
New hospitalization			X

#### 5. Ethical Aspects

Surveillance of patients with bacteremia is a routine activity of the Antimicrobial Stewardship Team in our hospital, that depends on the Sistema Aragonés de Salud. Demographical, clinical and microbiological data registry is part of this activity.

The study protocol has been reviewed and approved by the Comité Ético de Investigación Clínica de Aragón (CEICA): approval Number: P119/070

The enrollment of patients to determinate GZM A, gzmA gen polymorphisms will require signed informed consent.

#### 6. Planned Schedule

##### January to Jun 2019:

- Local Ethics Committee (CEICA) approval request: Compilation of administrative documentation and forms, including information sheet and informed consent
- Statistical consultation.
- Design of the case report form (CRF) and database
- Biobank arrangements.
- Recruitment of the study coordinator.
- Training of research staff.
- Clinical Trials Register.

##### July 2019 to August 2020.

- Screening and inclusion of patients with bacteremic (E. coli) UTIs.
- Data capture (demographical, clinical and basic laboratory parameters).

- Storage of patient samples and E. coli strains (blood and urine).
- GZM A determination.
- Whole exome sequencing (gzmA polymorphisms).
- Whole genome sequencing (E. coli strains).

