**September 2020 to December 2020.**

- Data analysis
- Manuscripts preparation.  
Manuscript submission.

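### The GZM A assay is scheduled alongside inclusion, when sepsis status and matched pairs must be decided, and its period can close before the last day-30 samples are drawn

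*Protocol*

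**What the plan says.** Section 6 gives one block, "July 2019 to August 2020", to several activities, among them "Screening and inclusion of patients with bacteremic (E. coli) UTIs", clinical data capture, storage of patient samples and "GZM A determination". The next block, "September 2020 to December 2020", lists only data analysis and manuscript work.

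Two statements in section 4.5 bear on the timing of the assay. One introduces a list that ends with GZM A: "The following biomarkers will be determined during patient enrollment". The other sets three sampling times: "GZM A serum levels will be obtained in all patients during the enrollment visit, the 2-3 day and the 30 day visits". The table in section 4.6 agrees, with serum and plasma at day 0, day 2-3 and day 30.

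Section 4.3 fixes 50 patients at a 1:1 ratio of sepsis to non-sepsis, matched on gender, age within 10 years, Charlson score within 1, and time from symptom onset to blood culture within 24 hours. Section 4.4 defines cases by reference to a consensus-conference definition and controls by its absence. Section 4.2 runs the study to December 2020.

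**The concern.** Sepsis status is the outcome and GZM A is the exposure under test. The operational hypothesis in section 2 is directional: GZM A is expected to be higher in patients who develop sepsis. If a borderline patient is classified, or a control is chosen from several who fit the calipers, by someone who has seen GZM A values, any influence would tend to favour that hypothesis. No analysis can undo this afterwards, because it is built into who counts as a case and who is paired with whom. The order of classification, pairing and assay is a matter of study conduct, and the protocol's own timetable sets it. It is therefore not a detail that can be left to an analysis plan.

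The second matter is the calendar. Day-30 GZM A is required in all patients and serves the kinetics objective (section 3.2). The block that contains the assay closes on the same date as inclusion, so it makes no allowance for the 30 days of follow-up of the last patients.

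**Working it through.** **Order of the steps.** The protocol states no sample-size or power figure that bears on this point, so the first check sets its statements side by side.

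1. Section 6 puts inclusion and the GZM A assay in the same 14 months. Section 4.5 points the same way by placing GZM A among the biomarkers determined at enrolment.
2. The schedule names neither case classification nor matching. Section 4.3, however, includes patients at a 1:1 ratio with matching on four factors. That quota can be filled only if each patient's status, and the availability of an eligible partner, are known while inclusion is running.
3. Section 4.4 gives no assessor and no time point for the status call. Section 4.3 gives no rule for choosing among several eligible controls, and the calipers are wide enough that more than one may qualify.
4. The protocol does not say that those who classify or match are blind to GZM A, that the laboratory is blind to status, or that the assay waits until status and pairing are settled.

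From 1 to 4, decisions on outcome and pairing can be made with exposure results known.

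**Calendar.** Inputs: the block July 2019 to August 2020 (section 6), read as first to last calendar day; the day-30 sample (sections 4.5 and 4.6); 50 patients (section 4.3). Even accrual is an assumption.

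- Length of the block: 184 days (July-December 2019) + 244 days (January-August 2020) = 428 days.
- Last day 0 whose day 30 falls inside the block: 31 August 2020 - 30 days = 1 August 2020.
- Entries from 2 to 31 August 2020 (30 days) have day 30 between 1 and 30 September 2020, after the block.
- Share of the block: 30/428 = 7.0%. Expected patients: 50 x 30/428 = 3.5.
- Chance of at least one such patient: 1 - (1 - 0.0701)^50 = 97%.

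| Accrual in the last 30 days | Expected patients with day 30 after the block | Chance of at least one |
|---|---|---|
| Half the even rate | 1.8 | 83% |
| Even rate | 3.5 | 97% |
| Twice the even rate | 7.0 | >99.9% |
| 50th patient enters by 1 August 2020 | 0 | 0 |

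The earlier samples are almost unaffected: the latest possible day-3 sample falls on 3 September 2020. The latest day-30 sample, 30 September 2020, leaves 92 days before the study period ends on 31 December 2020.

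**The case against.** The strongest reply is that the schedule is an unordered list covering 14 months. It puts sample storage next to the assay, which fits a single batch late in the block at least as well as patient-by-patient testing. The sentence in section 4.5 about determination during enrolment cannot literally fix the assay date, because the same section then requires GZM A at day 2-3 and day 30. GZM A is neither a matching factor nor, in these documents, part of the case definition. That definition defers to a consensus conference, and a sepsis score is scheduled. Plate layout and laboratory blinding often sit in a laboratory manual.

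Much of this stands. Sharing a calendar block does not prove that results are known when status is assigned. Still, a late batch is only possible under this text, not stated, and a batch run before inclusion closes would still precede the last classifications. The sepsis score is not named or tied to the case definition, so it does not close the gap.

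A reader might also infer three stronger things that the protocol does not support:

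- **That the assay is rolling, so that pair members or a patient's time points fall on different ELISA runs.** Nothing says so, and no assay precision is given from which to size any run-to-run noise.
- **That late kinetics lie outside the plan.** Day-30 sampling is required in all patients, and 30 September 2020 lies within the study period. Only the assay line in section 6 would be overrun.
- **That the dates conflict whatever happens.** The overrun arises only if someone enters after 1 August 2020. Inclusion is capped at 50 and may finish sooner.

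**Conclusion.** The point holds in this form. The protocol places the exposure assay in the period in which sepsis status and matched partners must be decided, and nothing in it prevents those decisions from being made with GZM A results known. This is an avoidable exposure to bias in a comparison of 25 against 25, not evidence that bias will occur, and its size cannot be computed from the documents. That classification and pairing fall in this period is an inference from the 1:1 matched inclusion, not a line in the schedule.

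The calendar part is smaller and conditional: about 3.5 of 50 patients under even accrual, between 0 and 7 across the cases tabulated, would have a day-30 sample due after the assay block but before the study ends. It rests on reading the months as whole calendar months and on inclusion being allowed to run to 31 August 2020. The change is worth making before the study starts, because the first part cannot be repaired at analysis.

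**What to change.** In section 6, take GZM A determination out of the July 2019 to August 2020 block. Make it a coded batch run after the last day-30 sample (by about 30 September 2020 if inclusion ends on 31 August) and after case/control status and pairing have been locked. State that the laboratory is blind to status. Where feasible, put both members of a pair, and all of a patient's time points, on the same plate. In section 4.5, reword the introduction to the biomarker list so that GZM A samples are collected, not assayed, at enrolment.

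The storage needed is already in the schedule. The cost is an edit to two sections, coded labels, results about one month later, and longer freezing: about 15 months for a sample taken on 1 July 2019 and assayed on 30 September 2020. The protocol gives no stability information for frozen GZM A, so the sponsor should confirm that this duration is acceptable. The assay would then fall within the September to December 2020 period and shorten the time left for analysis and manuscripts to 92 days.
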